In the United States (U.S.), selective serotonin reuptake inhibitors (SSRIs) have been the predominant method for treatment of adolescent depression for more than a decade [10]. Drug treatment of depression in youth has become standard practice, in part because of the failure of most evidence-based psychotherapy treatments to make their way into everyday practice [11]. Despite the increased attention to pediatric MDD sparked by the U.S. Food and Drug Administration's (FDA's) "Black Box" warning applied to antidepressants prescribed to children and adolescents [12], the pharmacological treatment options remain limited. In a systematic review of 13 randomized placebo-controlled trials for pediatric depression involving 2,750 participants, Usala and colleagues found a pooled response rate of 59.5% (95% C.I. 57.2–62.5) and a placebo response rate of 47.9% (95% C.I. 45.5–51.1) [13]. Combined risk differences in rates of antidepressant response status favored antidepressants over placebo by just 11.0 % (95% C.I. 7.1–14.9). Similarly, a recent study that specifically examined the placebo response in pediatric MDD trials found that the mean proportion of participants per study responding to placebo was 0.46 (S.D.=0.08; Range=0.33–0.57) [14].

The number needed to treat [15] (NNT) is an evidence-based medicine statistic that represents the relative benefit of treatment compared with the control condition. The NNT is the number of patients a clinician must treat to prevent one adverse outcome (e.g. unremitted depression in one patient). Tsapakis and colleagues conducted a meta-analysis of 30 randomized, placebo-controlled trials for pediatric depression. The NNT for antidepressants in pediatric MDD is 9.35 (95% C.I. 7.1-13.7) [16]. As a measure of treatment effect, the practical implication is that a practicing clinician must treat nine patients with antidepressants in order for one pediatric patient with MDD to recover who would otherwise not have. Meanwhile, the clinician must expose all nine patients to an approximate doubling of the risk for suicidal ideation or behavior [17]. With greater than 40% of pediatric MDD patients classified as antidepressant non-responders and a narrow therapeutic margin between antidepressants and placebo, new treatment options are urgently needed.

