use in child psychiatry is novel. Creatine's gender-specific effects in animal models mandate that studies in youth be initially limited to female participants. Expanding upon our group's recent completion of a multidose study to establish which of four daily creatine doses offers the best combination of efficacy, safety and tolerability in adolescent females with SSRI-resistant MDD, we propose to conduct a pilot, placebo-controlled study of 10g daily adjunctive creatine, the dose selected from the dose-ranging trial, for adolescent females with SSRI-resistant MDD. We propose to examine the relationship between depression severity and cerebral PCr and to measure the effect size of adjunctive creatine vs. placebo on brain chemistry and clinical outcome in adolescent females with SSRI-resistant MDD.

OBJECTIVES:

The primary hypothesis is that compared to placebo, 10g of daily creatine monohydrate for eight weeks will be associated with significant increases in frontal lobe PCr and β -NTP concentrations. A secondary hypothesis is that decreased depressive symptoms measured with the CDRS-R and Montgomery Asberg Depression Rating Scale (MADRS) will be reciprocally correlated with increased β -NTP concentrations.

PARTICIPANT SELECTION CRITERIA:

Thirty-three female adolescents with MDD will be randomly assigned in a 1:1 ratio to either treatment for eight weeks, for a total of 66 MDD participants. Additionally, 40 healthy adolescents will be recruited as comparison subjects for the study. Key inclusion, exclusion, and study withdrawal criteria for each subject group are summarized below.

MDD SUBJECTS

Inclusion Criteria:

- Participants must be female.
- Participants must be able to grant informed consent (age ≥ 18), or parent/guardian permission plus participant assent (age < 18).
- Participants must meet DSM-IV criteria for MDD, with current mood state depressed for > 2 weeks.
- Participants must be between the ages of 12 and 21.
- Current CDRS-R raw score of ≥ 40 or MADRS score ≥ 25 ; and CGI-S score ≥ 4 .
- Participants may be enrolled in individual and/or group psychotherapy, if it has been ongoing for at least 8 weeks.

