- Participants must have been in treatment with an SSRI for at least 8 weeks, the last 4 of which were at a dosage of ≥ 20 mg per day of fluoxetine or its equivalent, e.g. 20 mg per day of paroxetine, 20 mg citalopram, 10 mg escitalopram, or 100 mg sertraline. If the participant attempted, but could not tolerate, a dose comparable to 20 mg fluoxetine, they will be considered eligible. (This definition of "Adolescent SSRI Resistant Depression" is modified from the NIH-sponsored, \$17 million TORDIA Randomized Controlled Trial [<http://clinicaltrials.gov/ct2/show/NCT00018902>] [128].

Exclusion Criteria:

- Unstable co-morbid medical, neurological, or psychiatric disorder.
- Current DSM-IV criteria for substance abuse or dependence (excepting nicotine/cigarettes).
- Clinically significant suicidal or homicidal risk.
- Pre-existing renal disease.

- Proteinuria on baseline urinalysis testing.
- Pregnancy or breastfeeding.
- Sexually active and unwilling to practice contraception during the study.
- Contraindication to magnetic resonance imaging (e.g. ferromagnetic implant or claustrophobia)
- History of hypersensitivity to creatine.
- History of a previous failed therapeutic trial of creatine.
- Participants may be outpatients or inpatients, but incarcerated persons will be excluded because this study is not approved for "Research Involving Prisoners."
- More than 2 suicide attempts prior to the screening visit
- Participants who made a suicide attempt within 6 months prior to the screening visit

Study Withdrawal Criteria:

- Withdrawal of parental permission, participant informed consent, or participant assent.
- Onset of a psychotic disorder or bipolar disorder.
- Intolerable or clinically significant side effects to creatine.
- Worsening depression, as demonstrated by an increase in CDRS-R or MADRS score $>25\%$ from baseline.
- Positive pregnancy test.
- A significant change to the participant's medication or psychotherapy treatment from the regimen reported at their baseline/screening visit (e.g. the SSRI is discontinued).
- Incarceration, as the study is not approved to conduct "Research Involving Prisoners."
- If a clinically significant intracranial lesion is found by the Radiologist on a participant's baseline brain scan, they will be withdrawn from the study and referred for appropriate medical care.

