We hypothesize that at baseline, CDRS-R scores are negatively correlated with cerebral PCr in female adolescents with SSRI-resistant MDD. We also hypothesize that for participants whose MDD responds to creatine, change CDRS-R score will be inversely correlated with change in brain beta-NTP levels (i.e. participants who have a significant decrease in their CDRS-R score will show an increase in beta-NTP).

Both intent-to-treat (ITT; encompasses all participants who receive >1 dose of study drug) and protocol completer analyses will be performed. A participant completing 8 weeks of treatment and both ^{31}P -MRS scans will be considered a "completer." Data will be expressed as mean + standard deviation (SD). Group differences in demographic variables involving continuous data will be calculated using one-way analysis of variance. Between-group comparisons involving categorical variables will be assessed using Fisher's exact test for n x k contingency tables. A linear mixed model (LMM) will be used to account for the association between measurements (baseline and post-treatment) for each individual for the repeated measures analysis. Exploratory data analysis using non-parametric statistical tests (e.g., Wilcoxon Rank-Sum test and the Mann-Whitney U-test) will also be performed. Statistical significance will be defined at the two-tailed, 0.05 level. Stata 11 (StataCorp LP, College Station, TX) and SAS 9.2 (SAS Institute, Cary, NC) software will be used for statistical calculations. Confidence intervals for all estimated parameters will be constructed using a 95% level.

Power Analysis and Sample Size Calculations: Calculations are based on the open-label female adolescent SSRI-resistant MDD creatine data obtained at our site, and our adult creatine studies. All power calculations are two-tailed with an alpha level of 0.05, and were performed in the specialized software PASS (NCSS, Kaysville, UT). The minimum required sample size

satisfying our hypothesis is 30 creatine-treated, 30 placebo-treated, and 30 age-matched healthy controls. Assuming a 10% attrition rate for MDD subjects and a 30% attrition rate for healthy controls, we propose to enroll a total of 66 female adolescents with SSRI-resistant MDD and 40 healthy controls. The central hypothesis and power analysis for the R33 clinical trial are described below.

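### The symptom/beta-NTP correlation is unrestricted in the Objectives but worded only for creatine responders in Statistical Analyses, so its analysis population is not fixed

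*Combined protocol and SAP*

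**What the plan says.** The Objectives section gives the secondary hypothesis without naming a subgroup: "decreased depressive symptoms measured with the CDRS-R and Montgomery Asberg Depression Rating Scale (MADRS) will be reciprocally correlated with increased" beta-NTP concentrations. Two scales are named, and nothing limits the hypothesis to responders or to one arm.

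Statistical Analyses, the only place in the analysis text where the hypothesis returns, words it "for participants whose MDD responds to creatine, change CDRS-R score will be inversely correlated with change in brain beta-NTP levels". Its parenthetical gloss is that "participants who have a significant decrease in their CDRS-R score will show an increase in beta-NTP". MADRS is not mentioned there, and what counts as a significant decrease is not stated.

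The next paragraph defines the analysis sets: "Both intent-to-treat (ITT; encompasses all participants who receive >1 dose of study drug) and protocol completer analyses will be performed". A completer is defined by "A participant completing 8 weeks of treatment and both" scans. There is no responder set. The methods listed are ANOVA, Fisher's exact test, a linear mixed model for baseline and post-treatment values, and rank tests; none is assigned to this correlation. The section does promise that "Confidence intervals for all estimated parameters will be constructed using a 95% level".

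**The concern.** The two statements differ in population and in scale, and nothing else in the supplied text settles which governs. Response is not defined anywhere for this trial. The only percentage-change rule on these scales is the withdrawal criterion, "Worsening depression, as demonstrated by an increase in CDRS-R or MADRS score" above 25% from baseline, which concerns deterioration.

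Read literally, the Statistical Analyses sentence limits the correlation to participants chosen for a large fall in CDRS-R, and CDRS-R change is one of the two variables being correlated. Placebo participants drop out by definition, and so do creatine participants who did not improve. Response to creatine is also not observable in an individual: the background reports a 24% mean CDRS-R decrease on placebo in the dose-ranging study, so improvement while taking creatine is not the same as improvement because of it.

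The trial is described as a pilot meant to estimate effect size for a later efficacy trial. A selected and possibly attenuated estimate would therefore be carried forward. An undefined population and threshold can also be settled after the data are seen.

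**Working it through.** **No figure to reproduce.** The plan gives no expected correlation, response rate or power for this hypothesis. Its one power figure (86%) concerns the between-arm metabolite comparison. What follows illustrates the literal reading only.

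**Inputs from the documents.** 30 evaluable creatine participants (Power Analysis and Sample Size Calculations); two-sided alpha 0.05 (Statistical Analyses). For a plausible range of response, the background review of paediatric trials gives 47.9% on placebo and 59.5% on antidepressant. That is a different population, used only to set a scale: 0.479 × 30 ≈ 14 and 0.595 × 30 ≈ 18.

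**Assumptions.** True |r| = 0.5 (0.4 as a check); changes bivariate normal with one relation across participants; responders are the fraction p with the largest CDRS-R decreases.

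**Step 1, attenuation.** Let c = Φ⁻¹(p) and λ = φ(c)/p. The variance of CDRS-R change among those kept, relative to all, is v = 1 − cλ − λ². The correlation among those kept is r′ = ρ√v / √(1 − ρ² + ρ²v).

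- p = 0.479: c = −0.053, λ = 0.832, v = 0.352; r′ = 0.5 × 0.593 / √(0.75 + 0.25 × 0.352) = 0.297/0.915 = 0.324.
- p = 0.595: c = 0.240, λ = 0.651, v = 0.419; r′ = 0.5 × 0.647 / √(0.75 + 0.25 × 0.419) = 0.324/0.925 = 0.350.

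**Step 2, power and interval.** By Fisher's z, power ≈ Φ(atanh(r)√(n − 3) − 1.96), and the 95% CI is tanh(atanh(r) ± 1.96/√(n − 3)).

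| Population | n | Expected \|r\| | Power | 95% CI at expected \|r\| |
|---|---|---|---|---|
| Responders, p = 0.479 | 14 | 0.32 | 20% | −0.25 to 0.73 |
| Responders, p = 0.595 | 18 | 0.35 | 29% | −0.14 to 0.70 |
| All creatine | 30 | 0.50 | 81% | 0.17 to 0.73 |

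For n = 30: 0.549 × 5.196 − 1.96 = 0.894, and Φ(0.894) = 0.81.

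**Step 3, sensitivity.** With response anywhere from 30 to 70% (n = 9 to 21), expected |r| is 0.29 to 0.38 and power 11 to 39%. With true |r| = 0.4 and 14 to 18 responders, expected |r| is 0.25 to 0.27 and power 14 to 19%, against 60% in all 30. If response were defined on another scale correlating 0.7 with CDRS-R change (assumed), 0.5 would become about 0.42 to 0.43, with power 36 to 45%.

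**Step 4, the opposite model.** Suppose half the creatine arm responds, r = −0.5 within responders and 0 in the rest, beta-NTP means are equal, and CDRS-R change means lie d within-group SDs apart. The within-group covariance averages 0.5 × (−0.5) = −0.25 and the variance of CDRS-R change is 1 + d²/4. The all-creatine r is therefore −0.25/√(1 + d²/4): −0.20 at d = 1.5 and −0.12 at d = 3.5. By simulation, the half with the largest decreases gives −0.33 to −0.44 over the same range. With a 1 SD beta-NTP difference between the groups, the two estimates are about equal. Restriction can therefore lose signal or keep it, depending on which model is true.

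**The case against.** The strongest reply is that the sentence is loose wording. The parenthetical restates a direction, as the Objectives do, and the sets defined next are ITT and completers. On that reading nobody is excluded and there is no truncation. This is a fair reading, and the documents do not rule it out. A reader might infer that the plan commits to a responder-only analysis and that the correlation will be biased; the text does not support that. What stands is that the two statements conflict and the population is not named.

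A second reply is that the responder restriction may be the scientific question. The background describes an energy-metabolism pattern present in some patients and tied to treatment response. If the link exists only in responders, pooling them with non-responders dilutes it, as Step 4 shows. This also stands: attenuation is conditional on a common relation, and removing the restriction has a price.

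Third, MADRS has not been withdrawn. The Objectives name it and the schedule collects it, so its absence from Statistical Analyses is an omission. The baseline PCr correlation in the same paragraph also lacks a named coefficient, so the missing method is a general gap in the section.

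**Conclusion.** The point holds as an inconsistency between the Objectives and Statistical Analyses on population and scale, with no response threshold. It should be resolved before unblinding. The harm is conditional. If the correlation is run only in responders, and one relation holds across participants, a true |r| of 0.5 would be expected at about 0.32 to 0.35 with 20 to 29% power, against 81% in all 30 creatine participants. The true r, the response rate, normality and a sharp CDRS-R cut-off are all assumed. The loss of sample size and the exclusion of placebo and non-responders follow from the literal reading whatever the model.

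A reader might also infer that the trial's main result is compromised. It is not: the primary hypothesis is a randomised comparison of metabolite change, and nothing here touches it. This is a secondary, observational association, since beta-NTP change is itself measured after randomisation.

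**What to change.** Rewrite the Statistical Analyses sentence to agree with the Objectives:

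- **Main analysis (one only):** the association of change in CDRS-R with change in beta-NTP in all creatine-arm participants with both scans, with the coefficient or regression model named and a 95% CI.
- **Supporting:** the same for MADRS; the placebo arm; and the pooled estimate adjusted for arm.
- **Exploratory:** any responder-only estimate, with the response criterion fixed before unblinding, reported beside the main one.
- **Set:** say how participants with both scans relate to completers. The two differ only by anyone who stopped study drug yet had the week-8 scan. This may be few or none, as Table 1 schedules no early-termination scan.

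The cost is wording; CDRS-R, MADRS and both scans are already scheduled. Two downsides should be stated. If the investigators intend a responder-only link, the main estimate can be diluted (about −0.12 to −0.20 against −0.33 to −0.44 in the Step 4 mixture with no beta-NTP mean shift), which is why the responder estimate belongs beside it. If the link exists only under creatine, the pooled estimate has less power than the creatine arm alone (about 48% against 81% at |r| = 0.5), which is why it is supporting.

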In the open-label study, participants' Children's Depression Rating Scale (CDRS-R) scores were reduced by 44% [55]. Moreover, utilizing pre- and post-treatment brain scans we found that brain PCr concentrations increased with eight weeks of creatine supplementation when compared to a comparison group of non-depressed adolescent controls [55]. In the dose-ranging study, participants were randomly assigned to treatment from one of the four study drug groups for 8 weeks. Participants randomized to all creatine treatment groups showed greater decreases in CDRS-R scores, with reductions between 28-42%, compared to the CDRS-R scores of participants randomized to placebo, who showed a decrease of 24% [unpublished data]. Participants treated with 10g daily creatine showed the highest increases in frontal lobe PCr, and were the only participants showing post-treatment increases in frontal lobe beta-NTP. In both studies, creatine was well-tolerated, and participants experienced no suicide attempts or psychiatric hospitalizations over the 8-week trial. We observed no persistent or clinically significant abnormalities on serum or urine laboratory tests.

The neuroimaging and clinical results from the R21 study suggest that daily adjunctive treatment of 10g creatine is associated with the greatest change in PCr, and higher PCr is associated with lower depression scores. Therefore, the dose of creatine our data suggests is most likely to engage the neurochemical target is the 10g dose. At the same time, our data do not suggest that the 10g dose poses significantly greater risks to subjects compared with placebo, other than weight gain attributable to intracellular water.

The current protocol seeks to expand upon our previous work by opening recruitment on a pilot study of creatine 10g daily vs. placebo as a treatment for female adolescents with SSRI-resistant MDD. The purpose of the pilot study is twofold: A) to evaluate several aspects of the feasibility of creatine supplementation as a treatment for this population; and B) to estimate the

effect size of adjunctive creatine, to inform the design and implementation of a potential future efficacy trial.

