- The principal investigator retains the right to withdraw participants from the study without their permission, in the event they are unwilling or unable to maintain adherence to the research protocol.

HEALTHY COMPARISON SUBJECTS

Inclusion Criteria:

- Participants must be able to grant informed consent (age >18), or parent/guardian permission plus participant assent (age <18).
- Participants must be female.
- Participants must be between the ages of 12 and 21 years.
- Participants must not meet DSM-IV-TR criteria for a current psychiatric illness or substance use disorder.
- Participants must have a CDRS-R score ≤ 30 .

Exclusion Criteria:

- Unstable medical or neurological illness.
- Clinically significant psychiatric or substance use disorder.
- Pregnant subjects, due to the unknown effects of MRI/MRS scans on a fetus. In addition, women of childbearing potential who are unable or unwilling to practice contraception during the study will be excluded. Female participants who are of childbearing potential must have a negative urine pregnancy test before the MRI/MRS scan.
- Participants with a contraindication to MRI/MRS scanning, such as a metallic implant.

Study Withdrawal Criteria:

- Withdrawal of parental permission or participant assent.
- Onset of a psychotic disorder or depression.
- Positive pregnancy test.
- A significant change to the participant's medication or psychotherapy treatment from the regimen reported at their baseline/screening visit, unless directed by the principal investigator.

DESIGN:

The proposed study will use a randomized double-blind placebo-controlled design. Sixty-six participants will be randomly assigned in a 1:1 ratio to placebo or 10g of oral daily creatine monohydrate augmentation for eight weeks.

The study's design is consistent with the acceptable ethical justifications for the use of placebo controls outlined in the University of Utah Institutional Review Board's (IRB's) Investigator Guidance on Placebo Comparators (Version B0608). Specifically, this study fits situations #3, #4 and #5 of the Guidance:

- "*Participants are refractory to the available therapies by virtue of their past treatment history*" (#3): by definition, the proposed study will recruit female adolescents with SSRI-resistant a.k.a. treatment-refractory depression. To meet the study's inclusion criteria, participants must have failed an adequate trial of the standard-of-care intervention.

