MRI scans will be conducted twice: at the baseline visit, and following 8 weeks of treatment with study drug. The 3.0 Tesla Siemens whole-body clinical scanner (Siemens Medical Solutions, Erlangen, Germany) located within the University Neuropsychiatric Institute (UNI) will be used to acquire this data. Participants will first undergo a routine anatomic MRI protocol, which includes MRI images acquired in the axial and coronal planes. Specifically, the anatomic scan protocol consists of a T1 weighted structural scan (MPRAGE), and double-echo T2 weighted scan, and a Fluid Attenuated Inversion Recovery scan (FLAIR). The purposes of the MR anatomic screening session include screening subjects for gross structural abnormalities and acquiring images for use in brain cortical thickness measurements. Anatomic MRI examinations will be performed with a quadrature radio-frequency coil. After localization, anatomical imaging will be obtained using a T1-weighted, sagittal oriented 3D-Magnetization Prepared Rapid Gradient Echo (MPRAGE) sequence (TR/TE/TI 2100/3.97/1100 ms, matrix 256x256, FOV 256x256 mm, flip angle 12 degree, slice thickness 1.5 mm, slab 192 mm, bandwidth 190 Hz/pixel). Axial proton-density and T2 weighted images will be acquired to screen for brain structural abnormalities using 2D Double echo T2 weighted turbo spin echo (TSE) sequence (TR 7110 ms, TE 28/84 ms, FOV 240x210, slice thickness 3 mm, flip 150°, bandwidth 179 Hz/pixel). FLAIR sequence (TR/TE/TI 8000/90/2500 ms, slice thickness 5 mm, FOV 240x168, voxel size 0.8x0.6x5.0 mm, bandwidth 200 Hz/pixel, turbo factor 13) will be used to detect juxtacortical-cortical lesions. All anatomic MRI images will be read by a board-certified Radiologist to screen for structural abnormalities.

ii. Measurement of *In-Vivo* Brain Chemistry Using Phosphorus-31 Magnetic Resonance Spectroscopy (^{31}P -MRS)

a. Phosphorus MRS

Phosphorus spectroscopy data will be acquired on the same Siemens 3T system. We aim to keep the duration of each MRSI examination at or under 25 minutes. A 3D-MRSI sequence with elliptically weighted phase-encoding will be used to collect ^{31}P -MRSI data to minimize T2 signal decay. Acquisition parameters will be: data matrix size 16x16x8; TR 2000 ms; tip-angle 90 degree for hard RF pulse; Rx bandwidth ± 1 kHz; complex-points 1024; readout duration 256 ms; pre-acquisition delay 0.3ms; FOV 240x240 mm²; 16 NEX.

iii. Spectral Analysis of ^{31}P -MRS Data

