The hypothesis that PCr and beta-NTP levels measured with 31P-MRS will show significant change associated with 8 weeks of 10g daily creatine compared with placebo in female adolescents with SSRI-resistant MDD evaluates the significance of treatment-related recovery. In our open-label creatine data, we found that female adolescents with SSRI-resistant MDD showed increased PCr and decreased beta-NTP following creatine augmentation. The effect size of these changes were estimated to be approximately 1.0 (Cohen's d) with 10% SD. Therefore, when we conservatively set the effect size to be 0.9; sample size of 30 per each group; and common SD within a group of 10%, the changes of metabolite levels between creatine and placebo groups will be significantly (alpha level of 0.05) detectable with 86% of power.

ADMINISTRATIVE RESPONSIBILITIES

Resources:

The Brain Institute

The facilities at the University of Utah that are available for the proposed research include the following: the Brain Institute and UNI. The Brain Institute currently occupies 5,900 square feet of office and laboratory space in a building in the University of Utah Research Park adjacent to the Health Sciences campus. It also occupies clinical space in UNI, the site of the Brain Institute's Siemens 3T MRI research scanner.

Recruitment of Participants:

- No “cold calls” will be made by members of the study team.
- An informational flyer will be placed (with permission) on public bulletin boards. The flyer will be submitted to the IRB for approval prior to posting. Examples of public bulletin boards may include but are not limited to: University of Utah bulletin boards (for example, the Health Science Education Building, the College of Nursing, the Department of Psychology, etc.), the Salt Lake Community College, and business frequented by adolescents and their parents.
- An informational brochure has been created, to be displayed (with permission) in appropriate public areas, and to be provided to practicing mental health clinicians, pediatricians and family practitioners in the Salt Lake City area. The clinicians, at their sole discretion and without compensation, will pass the brochure to the parent(s) or guardian(s) of adolescent clients in cases where they deem it appropriate. The brochure will be submitted to the IRB for approval, prior to distribution to clinicians.

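### The mixed model has no stated contrast or baseline constraint; read as a change-score comparison it is valid but usually less precise than a baseline-adjusted one

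*Combined protocol and SAP*

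**What the plan says.** Under Statistical Analyses: "A linear mixed model (LMM) will be used to account for the association between measurements (baseline and post-treatment) for each individual". The plan adds nothing on fixed effects, the group-by-time term, baseline as a covariate, a constraint on baseline means, or the covariance structure. The sentence names no outcome, so it can be taken to cover the spectroscopy measures and the depression scales alike.

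The power paragraph describes what is to be detected: "common SD within a group of 10%, the changes of metabolite levels between creatine and placebo groups". It uses an effect size of 0.9 with 30 per group and states 86% power. On the tests: "All power calculations are two-tailed with an alpha level of 0.05".

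Under Neuroimaging Protocol: "MRI scans will be conducted twice: at the baseline visit, and following 8 weeks of treatment with study drug". Under DESIGN: "Sixty-six participants will be randomly assigned in a 1:1 ratio to placebo or 10g of oral daily creatine monohydrate augmentation". That section also places the first scan before any study drug is given. Under PARTICIPANT SELECTION CRITERIA: "Additionally, 40 healthy adolescents will be recruited as comparison subjects for the study". Table 1 gives the healthy group a single scan, at week 0.

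One of the pilot's two purposes, beside feasibility, is to estimate the "effect size of adjunctive creatine, to inform the design and implementation of a potential future efficacy trial". The summary before OBJECTIVES likewise proposes to "measure the effect size of adjunctive creatine vs. placebo on brain chemistry and clinical outcome".

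**The concern.** A mixed model with baseline as a repeated response can be fitted in two main ways. If each arm has its own baseline mean, the group-by-time term reproduces the comparison of change scores. If the randomised arms share one baseline mean, the model gives a baseline-adjusted comparison of week-8 values. Both are valid, but they usually differ in precision, and the plan does not say which is meant. The power paragraph points to the first.

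At stake is the width of the interval around the effect size. That matters here because the estimate is a stated product of the pilot and is intended to guide the design of a later trial. The baseline scan that would sharpen it is already being collected.

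**Working it through.** **Inputs.** From the protocol: 30 evaluable per arm, effect size 0.9, SD 10% (so a difference of 0.9 × 10 = 9 points), two-sided alpha 0.05, two scans. Assumed, because the protocol does not give them: rho, shown from 0.3 to 0.9, and the ratio k of the week-8 SD to the baseline SD, taken as 1 first and then varied.

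**The plan's own figure.** A two-sample t-test with d = 0.9 and 30 per arm has noncentrality 0.9 × √15 = 3.49 on 58 df. Its power is 92.9%, not the stated 86%. That mismatch is a separate matter and neither supports nor weakens this point.

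**Which contrast the model yields.** In a test fit on complete data, the unconstrained group-by-time model and the change-score comparison gave the same estimate (0.562) and the same standard error (0.302).

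**Variances with equal SDs (σ at both scans, n per arm).**
- Change contrast: (2/n) × 2σ²(1 − rho).
- Baseline-adjusted: (2/n) × σ²(1 − rho²) × [1 + 1/(2n − 4)]. The last factor is the cost of estimating the slope, and equals 57/56 at n = 30.
- Ratio, adjusted to change: (1 + rho)/2 × 57/56. At rho 0.5 this is 0.75 × 57/56 = 0.763. Its square root is 0.874, so the standard error falls by 12.6%.

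The n needed for the change contrast to match is 30 divided by the variance ratio.

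| rho | SE saved by adjusting | Excess SE of change contrast | n per arm for change contrast to match |
|---|---|---|---|
| 0.3 | 18.7% | 22.9% | 45 |
| 0.5 | 12.6% | 14.5% | 39 |
| 0.7 | 7.0% | 7.5% | 35 |
| 0.9 | 1.7% | 1.7% | 31 |

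**Checks by simulation** (30 per arm, true difference 9, SD of change 10). Over 40,000 trials per rho, the standard errors for change against adjusted were 2.593 vs 2.104, 2.589 vs 2.258, 2.566 vs 2.387 and 2.581 vs 2.536. Mean estimates were 8.98 to 9.01 for both methods, so neither is biased. Fitting both mixed models directly (unstructured covariance, 1,500 trials per rho) gave 2.60, 2.57, 2.55 and 2.62 unconstrained, against 2.11, 2.22, 2.40 and 2.55 constrained.

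**Unequal SDs.** The variance ratio becomes k²(1 − rho²)/(1 + k² − 2k·rho) × 57/56. Over rho 0.3 to 0.9, the standard error saved is:
- k = 0.8: 19.3% to 28.5%.
- k = 1.25: −0.9% to 10.6%.
- k = 1.5: −0.9% to 11.1%.

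The gain vanishes where k × rho = 1, because the change score then already uses the best slope. For example, at k = 1.25 and rho = 0.8 the ratio is 0.5625/0.5625 × 57/56. The largest expected loss is √(57/56) − 1 = 0.9%.

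**On the protocol's scale.** The plan does not say whether the 10% is the SD of change or of a single scan.
- If of change: SE = 10 × √(2/30) = 2.58 and the 95% half-width is 5.2 points. With adjustment the half-width is 4.2, 4.5, 4.8 and 5.1 across the four rho values. Power is 92.9% unadjusted and 98.8%, 97.5%, 95.8% and 93.6% adjusted.
- If of a single scan: unadjusted half-widths are 6.1, 5.2, 4.0 and 2.3, against 5.0, 4.5, 3.7 and 2.3 adjusted. Unadjusted power is 82.6%, 92.9%, 99.3% and over 99.9%.

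**The case against.** The strongest reply is that nothing is broken. A group-by-time mixed model is a legitimate analysis, and it matches the contrast on which the study was powered. On nearly every reading of the SD its power exceeds the stated 86%; the exception is a single-scan SD with rho 0.3, at 82.6%. If the authors meant a constrained baseline, nothing is lost. All of this stands, and it limits the point to efficiency.

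It is also fair that the size depends on two quantities the protocol omits. A reader might infer that adjustment always gains, or that rho alone sets the gain. The protocol does not support that: its common within-group SD says nothing about equality over time, and with a larger week-8 SD the gain can disappear.

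A reader might also infer that CDRS-R and MADRS have no between-arm model at all. That goes too far. The mixed-model sentence is not limited to metabolites; it is as unspecific for the clinical scales as for the scans.

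Finally, ANCOVA of the week-8 value has no outcome for participants without a second scan. The plan has an intent-to-treat analysis and assumes 10% attrition, so this objection holds against ANCOVA as the main analysis. It does not hold against the constrained mixed model, which keeps those participants.

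**Conclusion.** The point holds as one of efficiency. The plan leaves the contrast and the baseline constraint open, and its natural reading is a change comparison. Under equal SDs and 30 completers per arm, that comparison carries a standard error about 23%, 14%, 8% and 2% larger than a baseline-adjusted one at rho 0.3, 0.5, 0.7 and 0.9. These figures rest on an assumed rho, an assumed SD ratio and complete data.

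A reader might conclude that the planned test is biased, invalid or underpowered because of this choice. The protocol does not support that. Under the 1:1 randomisation the change contrast is unbiased with complete data, and it is the quantity the power paragraph describes. What is affected is the width of the interval for the effect size. The change is worth making because it costs almost nothing; the planned test does not depend on it.

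**What to change.** For PCr and beta-NTP, keep the planned mixed model and specify it:
- fixed effects for time and for arm at week 8, with baseline means constrained equal across the creatine and placebo arms;
- an unstructured covariance for the two scans;
- the week-8 between-arm difference as the primary contrast, with its 95% interval.

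The constraint must not extend to the healthy comparison group, which is not randomised. This form retains intent-to-treat participants who lack a second scan. In the completer analysis, ANCOVA of the week-8 value on arm and baseline is equivalent.

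State the same baseline-adjusted week-8 contrast for CDRS-R and MADRS. It would also help to give the assumed rho and to say whether the 10% is an SD of change or of a single scan.

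The cost is a few sentences in Statistical Analyses and one change to the model terms, with no new participants, visits or scans. The expected loss of precision is at most about 0.9% of the standard error, if the SDs and rho happen to make the change score already optimal.
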